8 INTERVENTION DISCONTINUATION

This study included behavioral intervention, which does not have any noted harm. Even though subjects may withdraw voluntarily from participation in the study at any time and for any reason. Participants should continue to be followed for outcomes, with their permission, even if the study intervention is discontinued. The replacement of subjects will not be made for those who withdraw or discontinue their participation in the study. RAs will collect safety data on any subject discontinued due to adverse events or serious adverse events and will be given appropriate care under medical supervision until the symptoms of any adverse events resolve or the subject's condition becomes stable. If voluntary withdrawal occurs, the subject will be asked to continue scheduled evaluations and complete an end-of-study evaluation. In any case, every effort will be made to undertake protocol-specified safety follow-up procedures.

9 STATISTICAL CONSIDERATIONS

9.1 Sample Size and Randomization

The pilot project aims to estimate the magnitude of the difference between the preventive intervention and the education control on the primary outcomes of interest (stress, anxiety, depressive symptoms) to inform the design of a large-scale intervention. A study comparing PMP to a treatment-as-usual control in Pakistan⁶¹ found a mean difference of about 7 points with a standard deviation of 8.5 on a measure of anxiety and depression for effect size ($ES=.86$). We do not expect our ES to be as large as what was observed in the Pakistani study⁶¹ given that we are doing a prevention trial and not an intervention study in a distressed population so that this study will provide an estimate of the ES of PMP as a preventive intervention.

We conducted a power analysis to detect an ES as small as $ES=.30$ with $\alpha = .05$ and power of $.80$. We may find a larger effect in our pilot, but our understanding is that power estimates should be based on the smallest effect that we want to detect rather than the size of the effect that we expect.⁶² We expect that families will average approximately 2-4 adult persons based on our pilot data, and conducted our power analysis to account for the correlation among family members. Analyses were conducted using Optimal Design,⁶³ which is power analysis software created for cluster randomized trials such as the present study. Accounting for the intra-correlation among family members of $.10$ and $\alpha = .05$, we would have 80% power to detect a standardized difference of $ES=.30$ between two treatment groups of 116 families (58 per treatment arm) with an equal probability of being randomized to each of our two intervention arms.

As noted above, we do not expect our ES to be as large as in the Pakistani study, but a sample of that size should be sufficient to provide the estimates of the differences between the conditions (with standard deviation in our sample) and the correlations between the targets specified by theory and our primary outcome of interest to inform the design of a larger-scale controlled trial. The other goal for the project is to determine whether the intervention affects the target mechanisms specified by theory to mediate or moderate the intervention's impact on the outcomes. Those estimates we will get from the correlation between our respective targets (coping and self-efficacy) and the primary outcomes.

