Anxiety and Depressive symptoms: The Hopkins Symptom Checklist-25 (HSCL-25)² will be used to measure anxiety and depressive symptoms experienced over the past month at baseline, post-intervention, and three-month post-intervention. It is composed of a 10-item subscale for anxiety and a 15-item subscale for depression, with each item scored on a Likert scale from 1 (not at all) to 4 (extremely).

Secondary outcome

Physiological stress: Cortisol hair-test (average hormone levels over the past three months) will be used as a biomarker to measure physiological stress. Neuroendocrine indicators, such as cortisol, are effective stress biomarkers because they are the first to respond to a given stressor and coordinate the physiological response of other bio-physiological systems.

Interventions and Duration

Study Arms:

Experimental: Problem Management Plus for Immigrants (PMP-I) at family settings

Active Comparator: Talk program with Community Support Service Pamphlet (CSS)

Assessment:

Baseline, Post-Intervention, and 3-month Post-Intervention

Intervention:

PMP-I is a 5-week, peer-led, culturally tailored psychoeducation, behavioral activation, and problem-solving (90 minutes), breathing and yoga intervention (90 minutes) in a family setting. PMP-I will use a structured approach, including once a week, face-to-face sessions, breathing, yoga practice, homework that includes recording activities, rebuilding individual skills, or learning new skills to reduce stress.

- 1. Managing Stress:** Breathing and yoga practices, stress-management sessions, and behavioral activation exercises to strengthen positive coping strategies.
- 2. Managing Problems:** Practice exercises to identify the problems, develop solutions, and plan a strategy to carry out those solutions.
- 3. Behavior Activation:** Communication skill sessions and practice exercises to identify and carry out pleasant tasks.
- 4. Strengthening Social Support:** Social skills session and practice exercise to identify social support.
- 5. Staying Well:** Make a plan that helps to create a supportive family environment.

Sample Size and Population

This study will be conducted among 226 Bhutanese adults settled in Massachusetts.

STUDY TEAM ROSTER

Principal Investigator: [name]., MPH, MPHC, CGM
Assistant Professor, College of Nursing, [name], University Massachusetts Amherst, MA, 01003
Email: [contact]
[contact]

Co-Investigator: [name].

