1 STUDY OBJECTIVES

1.1 Hypothesis: Immigrants in the Problem Management Plus for Immigrants (PMP-I) will have significantly lower stress and anxiety/depressive symptoms than immigrants in the talk program with Community Support Service pamphlets (CSS).

1.2 Objective: The current study aims to pilot test the feasibility and acceptability of PMP-I among Bhutanese immigrants 18 years and older living in Massachusetts.

Aim 1: Adapt and culturally modify PMP to develop PMP-I as a family-based preventative intervention.

- a) Develop a training guide and intervention curriculum;
- b) Obtain iterative feedback about the format, ease of use, and implementation barriers from participants, facilitators, and community members.

Aim 2: Test the feasibility, acceptability, and preliminary outcomes of PMP-I with trained community facilitators.

- a) Assess i) recruitment, session attendance, and retention rates and program acceptability using checklists from participants; ii) feasibility of measures for assessing inclusion/exclusion, the fidelity of intervention delivery, mediators of response, and outcomes using checklists from facilitators; and iii) barriers and facilitators of intervention using interview and focus group discussion with participants and facilitators.
- b) Test preliminary effects of PMP-I vs. talk program with community support services pamphlets (CSS) using a small randomized pilot trial (N=116 families; 58 families per intervention and control), on perceived stress, anxiety and depressive symptoms (primary), physiological stress assessed in hair cortisol (secondary), and self-efficacy and coping strategy, family wellbeing, and social networking (targets), with assessments at baseline, post-intervention, and 3-month post-intervention.
- c) Evaluate the relationships between targets and outcomes and explore mediators (e.g., coping) of intervention-outcome relation.

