4 SELECTION AND ENROLLMENT OF PARTICIPANTS

4.1 Inclusion Criteria

We plan to include eligible adults aged 18 or older interested in participating in the study as primary study participants. This includes parents and their adult children aged 18 and above. At baseline, we will use our screening tool to identify individuals without significant depressive symptoms, as we aim to evaluate the effect of our intervention to prevent depression, rather than treat depression.

Eligibility criteria for our primary study participants include Bhutanese adults 18 years or older (both parents and children of each family) resettled in Massachusetts with a score 14 or below on the Patient Health Questionnaire (PHQ-9), a screening questionnaire for depression. Our statistical analysis will focus on data from primary study participants only with baseline PHQ-9 scores 14 or below. However, all other interested adult family members, both parents and their adult children, regardless of PHQ-9 score, will be invited to participate in our study, to maintain the confidentiality of each family member's mental health status within their family.

Besides, individuals with PHQ-9 screening score '15-19' (moderately severe depression) and '20-27' (severe depression) will be provided with feedback on their screening questionnaire outcomes confidentially. They will be encouraged to consult their primary health care providers. A field supervisor can provide the necessary support for setting up an appointment with primary health care providers and emergency services, as needed. A field supervisor also will make a follow-up home visit to monitor their mental health condition, as necessary.

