families (58 families per intervention and control) using a random number table. For random allocation, first, PI will prepare the sampling frame that lists interested families. Second, assign a number to each family in the sampling frame. Third, select 116 numbers using a table of random numbers. PI will request any interested community member to point one number in the random number table by closing his/her eyes. Since the selected families total 116, or three digits, we will choose only the first three digits of the number chosen as the first sampled family. Finally, we will choose other numbers moving down the first number column until all 116 families will be selected.

We will assign a random number selected at the first attempt for intervention and the second attempt for control. It means random numbers selected at odd attempts (first, third, seventh,) will be assigned for intervention and at even attempts (second, fourth, sixth...) for control. The sample elements corresponding to the selected random numbers become the sample. Procedures are in place for tracking the participants for intervention and follow-up (e.g., contact address and phone). RAs will visit selected families and brief them about study procedures, informed consent, and procedures to protect human subjects. All adult members of selected families who meet the inclusion criteria and give informed consent will be recruited for the study. We will follow up with all families randomized to either study arm. We will not follow up with participants if they decide to end their participation at a particular time point of our study. But, we will include their already collected data in our analysis. Given our strong community networks and mobilization of community RAs, we anticipate low attrition rates in practice. Ethical approval for our study will be obtained from the Institutional Review Board at UMass Amherst.

Recruitment of focus group discussion participants

PI will collect data on engagement, acceptability, and satisfaction of intervention delivery by conducting focus group discussions (FGD) with selected interested participants who are already enrolled in our study from the intervention group (30) upon intervention completion using a brief guide questionnaire. The participant will be eligible to attend the focus group discussion if they are already enrolled in our intervention group and have attended our mental health promotion program. RAs will inform participants about FGD

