The primary analyses will test whether participants' outcomes in the PMP-I arm differ from those in the control arm. Multilevel modeling will compare outcomes of each treatment arm while accounting for the clustering of participants within families. Continuous outcomes will be analyzed using hierarchical linear modeling, and dichotomous outcomes will be analyzed using multilevel generalized linear models with a Bernoulli distribution appropriate to nonlinear binary outcomes.⁶⁴ We expect approximately 2-4 members for each of the 58 families in each treatment arm, and the correlation among family members' responses will be accounted for in the model. Hierarchical or multilevel modeling is suited to these data as it accounts for the clustering of members within families and unbalanced designs (i.e., different family sizes).⁶⁴ This will be an intention-to-treat type of analysis, as multilevel modeling allows retention of all participants irrespective of the number of sessions attended (multilevel modeling uses maximum likelihood estimation, one of the recommended ways of handling missing data). The analysis will estimate endpoint outcomes based on repeated measures (Level 1) within individuals (Level 2) within families (Level 3). This three-level model is represented by the following equations:

Level 1: $Outcome_{ijk} = \pi_{0jk} + \pi_{1jk} * Time_{ijk} + e_{ijk}$; Level 2: $\pi_{0jk} = \beta_{00k} + r_{0jk}$; $\pi_{1jk} = \beta_{10k} + r_{1jk}$
 Level 3: $\beta_{00k} = \gamma_{000} + \gamma_{001} * PMP-I_k + u_{00k}$; $\beta_{10k} = \gamma_{100} + \gamma_{101} * PMP-I_k + u_{10k}$

[figure not shown]

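### The stated 80% power for an effect size of .30 needs about four analysed adults per family (two-sided); at the synopsis figure of 226 adults it is about 57%

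*Combined protocol and SAP*

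**What the plan says.** Section 9.1 bases the sample size on a standardized difference of .30, alpha .05, an intra-family correlation of .10 and 116 families split equally between two arms. It concludes that "we would have 80% power to detect a standardized difference of" .30.

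On family size, section 9.1 gives only a range: "We expect that families will average approximately 2-4 adult persons based on our pilot data". Section 9.2 (Aim 2b) repeats it: "We expect approximately 2-4 members for each of the 58 families in each treatment arm". Neither names the value used in the calculation.

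The synopsis, under Sample Size and Population, gives a head count: "This study will be conducted among 226 Bhutanese adults settled in Massachusetts".

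Sidedness is not stated. Section 9.2 asks whether "outcomes in the PMP-I arm differ from those in the control arm", which reads as two-sided. The hypothesis in section 1.1 is directional: participants given PMP-I "will have significantly lower stress and anxiety/depressive symptoms than immigrants in the talk program".

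Two statements bear on how many adults are analysed. Section 4.1 says "Our statistical analysis will focus on data from primary study participants only with baseline PHQ-9 scores 14 or below", and section 4.2 also leaves out those with a diagnosed mental health problem. On loss to follow-up, section 4.3 says "we anticipate low attrition rates in practice", without a rate.

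**The concern.** Power in a cluster-randomized design depends on the number of clusters, the intra-cluster correlation and the number of members per cluster. Section 9.1 fixes the first two and leaves the third as a range, so the 80% cannot be checked as written. Whether it is true depends on where in the range the mean falls. The only head count in the documents lies just below that range.

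The power claim is used later. Section 9.2 expects the endpoint comparison to be statistically significant because of the power analysis. If true power is well under 80%, a null result could be over-read as evidence against the intervention. The number of adults also sets the precision of the effect-size estimate, which the plan calls its ultimate goal.

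**Working it through.** **Inputs.** From section 9.1: J = 116 families, effect size d = .30 (SD = 1), intra-family correlation ρ = .10, alpha = .05. From the synopsis: 226 adults, so m = 226/116 = 1.948 per family. From sections 9.1 and 9.2: m between 2 and 4, so 116 × 2 = 232 to 116 × 4 = 464 adults.

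**Formula.** For a two-arm cluster-randomized comparison of one endpoint measure,

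λ = J d² / {4 [ρ + (1 − ρ)/m]}

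Two-sided power comes from the noncentral F with 1 and J − 2 = 114 degrees of freedom. One-sided power comes from the noncentral t with 114 degrees of freedom and noncentrality √λ. The numerator is 116 × .09 = 10.44.

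**The plan's own figure.** At m = 4, λ = 10.44 / [4 × (.10 + .90/4)] = 10.44 / 1.30 = 8.03. Two-sided power is 80.2%, so the stated 80% is reproduced at the top of the range.

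**Across the range.**

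| Mean analysed adults per family | Adults | λ | Power, two-sided | Power, one-sided | Effect detectable at 80%, two-sided |
|---|---|---|---|---|---|
| 1.95 (synopsis) | 226 | 4.64 | 57.0% | 69.1% | .39 |
| 2 | 232 | 4.75 | 57.9% | 69.9% | .39 |
| 3 | 348 | 6.53 | 71.7% | 81.4% | .33 |
| 4 | 464 | 8.03 | 80.2% | 87.9% | .30 |

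**Mean family size needed for 80%.** Two-sided: 3.97, or 116 × 3.966 ≈ 460 adults. One-sided: 2.84, or 116 × 2.838 ≈ 329 adults. The 226 adults reach 80% under neither reading. Setting the intra-family correlation to zero does not change that: 61% two-sided, 72% one-sided.

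**Simulation check (8,000 runs).** With 110 families of two and six of one (226 adults), power was 56.4% two-sided and 68.7% one-sided. With 116 families of four it was 81.2% two-sided.

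**Precision.** The expected 95% CI half-width for the standardized difference is t(.975, 114) × √{4[ρ + (1 − ρ)/m]/J}. It is .276 at 226 adults, .233 at m = 3 and .210 at m = 4.

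**Attrition.** No rate is given, so this is an assumption: 10% to 20% of adults contribute no data to the analysis. Multiplying m by .9 and .8 gives two-sided power of 53% and 49% from 226 adults, 68% and 64% from m = 3, and 77% and 74% from m = 4.

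**The case against.** The strongest reply is that 80% is not a miscalculation: it is right at four adults per family, a value inside the stated range. That stands. The faults are an undisclosed input at its most favourable end and a head count that conflicts with it. An average expected to lie somewhere between 2 and 4 does not justify planning on 4.

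The 226 appears only in the synopsis, and the documents do not say whether it counts all adults or only those in the main analysis. This also stands, so the 57% is conditional on that figure. Without it, a mean of 3 still gives only 72% two-sided.

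The planned model uses three repeated measures, whereas the formula treats the endpoint as a single measurement. The effect is small. The documents give no within-person correlation. Assuming values of .4 to .8, a random-intercept model and linear time, 57% at 226 adults becomes about 57-61%.

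The attrition figures assume that all data from lost adults are missing, while the plan keeps data already collected and uses maximum likelihood. That criticism is fair. Under the same assumed correlations, if adults miss only the final visit, power at 226 adults is about 56-59% with 10% loss and 53-56% with 20%. At four per family, 20% loss gives about 77-80%. The attrition figures above are therefore a pessimistic bound.

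Finally, this is a feasibility pilot, and no decision rule in the documents depends on significance. That limits the weight of the point. But the plan makes the power claim itself and draws an expectation from it.

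**Conclusion.** The concern holds. On the inputs in section 9.1, the stated 80% is met two-sided only at a mean of about 4 analysed adults per family (about 460 adults), and one-sided only at about 2.8 (about 329). If the synopsis figure of 226 stands, power is about 57% two-sided or 69% one-sided. A true effect of .30 would then be missed about 43% of the time two-sided, against the 20% implied, and the CI half-width would be about .28, against .21 at four per family.

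These figures rest on the plan's correlation of .10, a single-endpoint comparison and no attrition. Repeated measures would raise them slightly. Attrition would lower them, as would the section 4.1 and 4.2 exclusions if 226 counts all enrolled adults.

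**What to change.** Restate section 9.1, with no added enrolment:

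1. State the mean number of analysed adults per family and the sidedness behind the 80%.
2. Reconcile 226 with 116 families of 2-4 adults (232-464), and say whether 226 counts only adults in the main analysis.
3. Give power at the reconciled number and at means of 2, 3 and 4, net of a stated attrition assumption, with the expected confidence interval width. Say whether lost adults are assumed to contribute no data or only to miss later visits.
4. In section 9.2 (Aim 2b), remove or qualify the sentence that expects a significant endpoint difference because of the power analysis.

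The cost is protocol wording only; enrolment and analysis do not change. The stated power may become less favourable.

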9.2 Data Analyses

Baseline and follow-up data will be entered into an Excel database and exported to SAS statistical package for analyses. Privacy and security rules will be applied to protect the confidentiality and security of the data. Security features will be used at multiple levels, including the data element, user, application, and hosting services, with password protection for data access monitoring. These features will ensure control of access, authentication of users, and transmission security. The field team will be trained in project data maintenance.

Aim 2a Feasibility assessment: The PMP provides specific guidelines for evaluating and monitoring the intervention that we will use to monitor intervention delivery's fidelity. These tools are PMP Quiz, PMP Helper's Supervision Form, PMP Helper Classroom-based Competency Assessment, PMP Helper In-field based Competency Assessment, PM+ Trainer/Supervisor Competency Assessment, and Session-by-Session Checklists for PMP Helpers. Using these standard tools, we will evaluate session-by-session classroom and in-field based competencies of participants, community trainers, and supervisor and provide them feedback as needed using supervision forms, role-plays, group discussion, and training.

Community field supervisors will collect data on eligibility, recruitment and enrollment, intervention session attendance (including reasons for missed sessions), and compliance with data collection procedures, including hair sample collection and anthropometric measurements using a checklist. They will monitor intervention sessions using WHO standard checklists. Items include adherence to the manual, percent of intervention content administered, proper use of time/materials, and adequate response to participants' questions. They will also collect data on engagement, acceptability, and satisfaction via brief questionnaires and focus group discussions (FGD) with participants and interventionists after each session and upon intervention completion. The PI will conduct FGD in the Nepali language with interventionists, supervisors, and participants separately to collect information on barriers and facilitators of intervention, perceptions about whether the intervention met participants' needs, and feedback on how effectively the program team worked with participants. Interviews and FGD will be documented verbatim in a written transcript for subsequent analysis. All qualitative data will be analyzed using thematic

content analysis.⁵³ Feedback provided by the field staff will be reviewed and coded to identify recurrent themes regarding the intervention's acceptability. All analyses will be conducted in the Nepali and translated into English. Fidelity data will be used to assess intervention content and transmission. We will determine retention by obtaining proportions of participants attending all or portion of sessions.

Aim 2b Intervention efficacy: We will carry out data management and descriptive analyses for study outcomes. Means, standard deviations, and percentile distributions will be used to describe the continuous baseline variables. Frequencies and percentages will be used to describe categorical variables. We will compare baseline characteristics of intervention and control groups using chi-square and t-tests as appropriate. While differences between groups are not expected because of the randomization used in the study design, variables showing significant differences between the two groups will be included as covariates in primary analyses. We will compare participants' characteristics to follow-up to those with complete data to assess potential limitations in recruitment and retention.

The primary analyses will test whether participants' outcomes in the PMP-I arm differ from those in the control arm. Multilevel modeling will compare outcomes of each treatment arm while accounting for the clustering of participants within families. Continuous outcomes will be analyzed using hierarchical linear modeling, and dichotomous outcomes will be analyzed using multilevel generalized linear models with a Bernoulli distribution appropriate to nonlinear binary outcomes.⁶⁴ We expect approximately 2-4 members for each of the 58 families in each treatment arm, and the correlation among family members' responses will be accounted for in the model. Hierarchical or multilevel modeling is suited to these data as it accounts for the clustering of members within families and unbalanced designs (i.e., different family sizes).⁶⁴ This will be an intention-to-treat type of analysis, as multilevel modeling allows retention of all participants irrespective of the number of sessions attended (multilevel modeling uses maximum likelihood estimation, one of the recommended ways of handling missing data). The analysis will estimate endpoint outcomes based on repeated measures (Level 1) within individuals (Level 2) within families (Level 3). This three-level model is represented by the following equations:

Level 1: $Outcome_{ijk} = \pi_{0jk} + \pi_{1jk} * Time_{ijk} + e_{ijk}$; Level 2: $\pi_{0jk} = \beta_{00k} + r_{0jk}$; $\pi_{1jk} = \beta_{10k} + r_{1jk}$
 Level 3: $\beta_{00k} = \gamma_{000} + \gamma_{001} * PMP-I_k + u_{00k}$; $\beta_{10k} = \gamma_{100} + \gamma_{101} * PMP-I_k + u_{10k}$

[figure not shown]
Where the outcome is measured at each repeated measure *i* for each individual *j* within each family *k*. Time is centered at the endpoint, so that β_{00k} estimates the value of the outcome for each family at the end of the study, informed by all data points available for that family. If an endpoint observation is missing due to drop out, the advantage of multilevel modeling is that it utilizes maximum likelihood estimation, which estimates the expected outcome for that cluster using information from prior assessments as well as the expected value from the entire model. The key test of difference in the outcome between the treatment groups is represented by γ_{001} (in bold); this is a test of difference in outcome at endpoint between families randomized to PMP versus not. We expect this test of difference to be statistically significant based on our power analysis for the difference in outcome *level* at the endpoint. Note that this model will also test group differences in *change* in each outcome (γ_{101}). While our pilot is not powered for the significance of effects of change over time, we will be able to obtain estimates of ES for change for use in future larger-scale trials and analyses.

The ultimate goal of our analyses is to estimate the ES for this prevention trial for each outcome, to inform our planning of a full-scale trial. As noted earlier, we have powered this pilot prevention trial with a conservative estimate of effect size based on a similar study in a clinical population, but no known studies have characterized the precise effect size of PMP as a preventive intervention; a goal of our pilot is to estimate the expected effect on the population of interest (i.e. an at-risk vs clinical population). All analyses will be performed using SAS, version 9 (SAS Institute Inc, Cary, NC).

Aim 2c Mediating effects: Separate models will be created to evaluate the relationships between mediators (targets) and outcomes and to explore mediators (e.g. coping) of intervention-outcome relation.

In this aim, we aim to test the potential *mediators* of the treatment-outcome association by conducting mediational analyses in a multilevel regression framework.⁶⁵ Following current

[figure not shown]
Figure 1 Mediational Analysis Framework

recommended best practices in mediational analysis, we will conduct these analyses using recommended practices for mediation with a multilevel framework.⁶⁶⁻⁶⁸

Figure 1 provides a visual representation of our proposed analyses, in which treatment is a predictor of treatment targets or mechanisms (i.e. the mediators such as coping), which are in turn associated with outcomes. As reviewers 1 and 3 note, in mediational analyses, variables must be measured in *temporal sequence*.

Figure 2 provides a visual representation of our proposed temporal sequence of variable measurement for mediational analyses, in which treatment randomization occurs before mediator target measurement, which in turn are collected before the outcome measure used in the proposed analyses. Second, it is crucial to test the *indirect effect* (a*b paths) of the treatment on the outcome through the hypothesized mediators. As the indirect

effect is not normally distributed, we will assess its significance via Monte Carlo simulated confidence intervals, which are the recommended counterpart in multilevel mediation to bootstrapped confidence intervals used in single-level analyses.⁶⁶⁻⁶⁸

Each potential mediational sequence will be tested in this manner (see **Table 1** for mediators and outcomes to be tested). While we acknowledge that mediational analyses are difficult to adequately power in a sample of our proposed size,⁶⁷ we believe these preliminary analyses will help identify potential mechanisms for our treatment effect. If baseline differences in treatment groups are found in either the mediating or outcome variables, baseline measures will be controlled for in all analyses. Sample mixed-format multilevel equations are provided below, where the nesting of measures (i) within families (j) is accounted for by the random effects u_{0js} : γ_{01} in the Mediator equation is the ‘a path’, and γ_{10} in the Outcome equation is the ‘b path.’

Table 1 Mediators and Outcome Variables

Mediators (Targets)	Outcomes
Coping, Self-Efficacy	Perceived Stress
Family or Social Support	Physiological Stress
Family Conflict Resolution	Anxiety Symptoms
Family Satisfaction	Depressive Symptoms
Family or Social Network	

$$T2Mediator_{ij} = \gamma_{00_Med} + \gamma_{01_Med} * TreatmentCondition_j + u_{0j_Med} + r_{ij_Med}$$

$$T3Outcome_{ij} = \gamma_{00_Out} + \gamma_{10_Out} * T2Mediator_{ij} + \gamma_{01_Out} * TreatmentCondition_j + u_{0j_Out} + r_{ij_Out}$$

The key estimates are the association of the treatment condition with the mediator (γ_{01_Med} , a path) and the association of the T2 mediator with the T3 Outcome (γ_{10_Out} , b path).

Multiplied together, these coefficients form the indirect effect of the treatment on the outcome and are tested for significance via Monte Carlo simulated confidence intervals. All analyses will be performed using Mplus, version 8.⁶⁹

